8.3.1 Adverse Error Monitoring and Reporting

Adverse effects related to infigratinib therapy will be monitored using a custom database and aggregate reports of AE (including type, CTCAE grade, duration, attribution and outcome) will be reported to the OSU DSMC, per policy.

8.3.2 Data Safety Monitoring Plan

Continuous evaluation of safety, data quality and data timeliness will be carried out. The PI will conduct continuous review of data and patient safety at their regular disease group meetings (at least monthly) and the discussion will be documented in the minutes. The PI of the trial will review toxicities and responses of the trial where applicable at these disease group meetings and determine if the risk/benefit ratio of the trial changes. Frequency and severity of adverse events will be reviewed by the PI and compared to what is known about the agent/device from other sources; including published literature, scientific meetings and discussions with QED Therapeutics, to determine if the trial should be terminated before completion.

Serious adverse events and responses will also be reviewed by the OSUCCC –James Data and Safety Monitoring Committee (DSMC). The PI will also submit a progress report (quarterly) that will be reviewed by the committee per the DSMC plan. All reportable serious adverse events will also be

reported to the Institutional Review Board (IRB) of record as per the policies of the IRB.

A mandatory monthly trial and safety review teleconference will be held for all participating sites. It will be expected that representatives from all participating sites be present for each call. Meeting minutes will document the attendance and discussions. Safety related information and data completion status will be minimally reviewed each month.

9. Data collection and management

9.1 Data confidentiality

Information about study subjects will be kept confidential and managed under the applicable laws and regulations. Those regulations require a signed subject authorization informing the subject of the following:

- What protected health information (PHI) will be collected from subjects in this study
- Who will have access to that information and why
- Who will use or disclose that information
- The rights of a research subject to revoke their authorization for use of their PHI.

In the event that a subject revokes authorization to collect or use PHI, the investigator, by regulation, retains the ability to use all information collected prior to the revocation of subject authorization. For subjects that have revoked authorization to collect or use PHI, attempts should be made to obtain permission to collect follow-up safety information (e.g. has the subject experienced any new or worsened AEs) at the end of their scheduled study period.

The data collection system for this study uses built-in security features to encrypt all data for transmission in both directions, preventing unauthorized access to confidential participant information. Access to the system will be controlled by a sequence of individually assigned user identification codes and passwords, made available only to authorized personnel who have completed prerequisite training.

Prior to entering key sensitive personally identifiable information (Subject Initials and exact Date of Birth), the system will prompt site to verify that this data is allowed to be collected. If the site indicates that country rules or ethics committee standards do not permit collection of these items, the system will not solicit Subject Initials. Year of birth will be solicited (in the place of exact date of birth) to establish that the subject satisfies protocol age requirements and to enable appropriate age-related normal ranges to be used in assessing laboratory test results.

9.2 Source documents

Before study initiation, at a clinical site initiation visit or at an investigator's meeting, The OSU PI and Multi-Site Team will review the protocol and CRFs with the investigators and their staff.

The investigator teams will maintain source documents for each patient in the study, consisting of case and visit notes (hospital or clinic medical records) containing demographic and medical information, laboratory data, electrocardiograms, and the results of any other tests or assessments. All information recorded on CRFs must be traceable to source documents in the patient's file. The investigator must also keep the original signed informed consent form (a signed copy is given to the patient).

The investigator teams will be responsible for confirming consistency between relevant source documents and the CRF entries. This includes full verification for the presence of informed consent, adherence to the inclusion/exclusion criteria and documentation of SAEs.

9.3 Data collection

For studies using Electronic Data Capture (EDC), the designated investigator staff will enter the data required by the protocol into the Electronic Case Report Forms (eCRF). The eCRFs have been built using fully validated secure web-enabled software that conforms to 21 CFR Part 11 requirements. Investigator site staff will not be given access to the EDC system until they have been trained. Automatic validation programs check for data discrepancies in the eCRFs and, allow modification or verification of the entered data by the investigator staff.

The Principal Investigator is responsible for assuring that the data entered into eCRF is complete, accurate, and that entry and updates are performed in a timely manner.

Biomarker (blood and tissue) samples obtained during the course of the study will be collected from the Investigator sites and sent to The Ohio State University Study Team (Tumor and Blood Manual). Designated investigational site staff will enter the information required by the protocol into the appropriate eCRF and/or designated laboratory requisition forms. Remote or field monitors may review the eCRFs and laboratory paper requisition forms for accuracy and completeness and instruct site personnel to make any required corrections or additions. One copy of the requisition form will be forwarded to each analytical laboratory with the respective sample(s) by a remote or field monitor or by the designated investigational site staff; and one copy will be retained at the investigational site.

9.4 Database management and quality control

For studies using eCRFs, The Ohio State University Multi-Site Clinical Trial Team will review the data entered by investigational staff for completeness and accuracy. Electronic data queries stating the nature of the problem and requesting clarification will be created for discrepancies and missing values and sent to the investigational site. Designated investigator site staff are required to respond promptly to queries and to make any necessary changes to the data.

Concomitant treatments and prior medications entered into the database will be coded using the WHO Drug Reference List, which employs the Anatomical Therapeutic Chemical classification system. Medical history/current medical conditions and adverse events will be coded using the Medical dictionary for regulatory activities (MedDRA) terminology.

10. Statistical methods and data analysis

The primary objective of this open label phase II study is to evaluate the efficacy of single agent Infigratinib in terms of overall response rate (ORR) in three cohorts of patients with solid tumor, FGFR fusions/mutations and failed standard of care (SOC):

- Cohort 1: Solid tumor patients with *FGFR1-3* fusion/translocation (**n, up to 30**) who have progressed on or are intolerant to SOC therapies. Prior therapy with a different FGFR inhibitor is not permitted.
- Cohort 2: Solid tumor patients with *FGFR1-3* fusion/translocation (**n=10**) who have progressed on or are intolerant to SOC therapies and received treatment with a different FGFR inhibitor.
- Cohort 3: Solid tumor patients with genetic alterations such as point mutations, insertions/deletions, or amplifications in any FGFR gene family member (**n=10**). Prior therapy with a different FGFR inhibitor is not permitted.

The data from participating centers in this protocol will be combined. Data will be summarized with respect to demographic and baseline characteristics, efficacy and safety observations. Categorical data will be presented as frequencies and percentages. For continuous data, mean, standard deviation, median, 25th and 75th percentiles, minimum, and maximum will be presented.

For all analyses, data from patients from each cohort will be analyzed separately, unless otherwise stated.

10.1 Sample size and power calculation

For Cohort 1, the Simon optimum two-stage design is used to evaluate the primary endpoint of overall response rate in this patient population (Simon 1989; Simon et al. 2016). In this relapsed/refractory population of advanced solid tumor patients identified as having genomic fusion in *FGFR1-3*, our null hypothesis is that if the treatment is not active then the overall response rate will be at most 5%, reflecting a response by chance alone. We hypothesize that for this treatment, an ORR of at least 25% would be considered promising in this patient population. This study is designed to detect an ORR of at least 25% vs. $\leq 5\%$. After evaluating 9 patients enrolled in the first stage, the trial will be terminated if 0/9 patients demonstrate a response. If the trial goes on to the second stage, a total of 30 evaluable patients will be enrolled. If the total number responding is 4 or more, then the drug demonstrates promising response in this patient population. This design has 90% power and 5% type I error.

For Cohort 2 and 3, with $n=10$ evaluable patients, the estimated ORR with corresponding 90% Confidence Interval for various number of responses are listed below:

Responses	ORR	90% CI
0	0	(0.0, 0.206)
1	0.1	(0.005, 0.394)
2	0.2	(0.037, 0.507)
3	0.3	(0.087, 0.607)

4	0.4	(0.150, 0.696)
5	0.5	(0.222, 0.778)
6	0.6	(0.304, 0.850)
7	0.7	(0.393, 0.913)
8	0.8	(0.493, 0.963)
9	0.9	(0.606, 0.995)
10	1	(0.794, 1.000)

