Data analysis	Data will be collected and analyzed centrally by the Clinical Trials Office at The Ohio State University. It is planned that the data from participating centers in this protocol will be combined, so that an adequate number of patients will be available for analysis. Data will be summarized with respect to demographic and baseline characteristics, efficacy and safety observations. Categorical data will be presented as frequencies and percentages. For continuous data, mean, standard deviation, median, 25th and 75th percentiles, minimum, and maximum will be presented. For all analyses, data from patients with FGFR1-3 gene fusions/translocations and from patients with other FGFR genetic alterations will be summarized separately, unless otherwise stated. The estimated ORR along with the corresponding 90% confidence interval will be presented for each cohort. OS and PFS will be estimated using the Kaplan Meier method. For Cohort 1, a Simon optimum two-stage design is used to detect an ORR of at least 25% vs. ORR \leq 5% in this patient population. After evaluating 9 patients in the first stage, the trial will be terminated if 0/9 patients demonstrate a response. If at least 1 of 9 patients has CR or PR, a total of 30 evaluable patients in Cohort 1 will be enrolled.
Key words	Infiratinib, advanced solid tumors, FGFR1-3 gene fusion/translocation, FGFR genetic alterations, RECIST v1.1

1. Background

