10.4 Efficacy analysis

10.4.1 Primary endpoint: ORR

Analysis of the efficacy primary endpoint (ORR) will be conducted when all patients have completed at least 6 cycles of treatment or have discontinued from the trial. Any PR or CR until the data cut-off date will be considered as a responder for ORR, irrespective of when it occurred. The following analysis will be done for each cohort of patients.

The estimated ORR will be presented along with the corresponding 90% confidence interval for each cohort, based on a binomial distribution.

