10.4.2 Secondary efficacy endpoints

Overall survival

Overall Survival (OS) is defined as the time from the date of start of treatment to the date of death due to any cause. The survival time for patients without documentation of death prior to the data cutoff, will be censored at the last date the patient was known to be alive prior to the cutoff date. Survival time for patients with no post-baseline survival information will be censored at the date of start of treatment. OS will be analyzed using the Kaplan Meier method. Survival rate at 4, 6, 8, 12, 18 and 24 months and median OS will be estimated along with 95% confidence intervals from the Kaplan Meier distribution. The FAS will be used.

Progression Free Survival

Progression free survival (PFS) is defined as the date of the start of treatment to the date of the event defined as the first documented progression or death due to any cause. If patient has not had an event, progression-free-survival is censored at the date of last adequate tumor assessment. Kaplan-Meier analysis of PFS will be conducted for each cohort.

Best Overall Response and Disease Control Rate.

Overall lesion assessments will be listed by patient. Best overall response (BOR) will be summarized for the each cohorts using the Overall Response Rate and the Disease Control Rate which are the proportion of patients having respectively a best overall response of PR or CR, or SD, PR or CR. The estimated ORR and corresponding 90% confidence intervals based on the binomial distribution will be reported.

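### The Cohort 2/3 interval table puts 5% in each tail for 1 to 9 responses but the full 10% in one tail at 0/10 and 10/10, without saying so under its single 90% CI label

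*Combined protocol and SAP*

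**What the plan says.** Section 10.1 tabulates the precision expected in Cohorts 2 and 3 for each possible count out of 10. The lead-in reads "the estimated ORR with corresponding 90% Confidence Interval for various number of responses are listed below", and all eleven rows share one column headed as a 90% interval. The end rows are printed as (0.0, 0.206) for no responses and (0.794, 1.000) for ten. No footnote gives any row a different level, sidedness or method.

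The method is not named elsewhere. The Protocol Summary (Data analysis) says "The estimated ORR along with the corresponding 90% confidence interval will be presented for each cohort". Section 10.4.1 says "The estimated ORR will be presented along with the corresponding 90% confidence interval for each cohort, based on a binomial distribution". Section 10.4.2 repeats the interval under best overall response: "The estimated ORR and corresponding 90% confidence intervals based on the binomial distribution will be reported". The reader learns the level and the distribution, but not the interval method or how the tails are handled when the count is 0 or n.

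**The concern.** A column of intervals at one level for one sample size should come from one stated rule. Here the limits at 0 and 10 are tighter than the rule behind the other nine rows would give, and nothing tells the reader that the rule has changed.

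Response rate is the primary endpoint in all three cohorts. For Cohorts 2 and 3 the estimate with its 90% interval is the only inference planned for it. Since sections 10.4.1 and 10.4.2 name no method, the table is the analyst's only guide to the intended one. What is at stake is whether that guide delivers the 90% on its label, and whether the interval for 0/10 is fixed in advance by a rule that someone has written down.

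**Working it through.** **Inputs.** n = 10, level 90%, and the eleven printed rows, all from section 10.1.

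**Step 1: reproduce the rows for 1 to 9 responses.** Two-sided Clopper-Pearson limits with 5% per tail are: lower = 0.05 quantile of Beta(x, n−x+1); upper = 0.95 quantile of Beta(x+1, n−x).

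| Responses | Printed | Computed |
|---|---|---|
| 1 | 0.005, 0.394 | 0.0051, 0.3942 |
| 2 | 0.037, 0.507 | 0.0368, 0.5069 |
| 3 | 0.087, 0.607 | 0.0873, 0.6066 |
| 4 | 0.150, 0.696 | 0.1500, 0.6965 |
| 5 | 0.222, 0.778 | 0.2224, 0.7776 |
| 6 | 0.304, 0.850 | 0.3035, 0.8500 |
| 7 | 0.393, 0.913 | 0.3934, 0.9127 |
| 8 | 0.493, 0.963 | 0.4931, 0.9632 |
| 9 | 0.606, 0.995 | 0.6058, 0.9949 |

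All 18 limits agree to three decimals (largest difference 0.0005).

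**Step 2: apply the same rule to the end rows.**
- 0/10: upper = 1 − 0.05^(1/10) = 0.2589. Printed: 0.206.
- 10/10: lower = 0.05^(1/10) = 0.7411. Printed: 0.794.

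The difference is 0.2589 − 0.2057 = 0.0532 at each end.

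**Step 3: find the rule behind the printed end rows.** With all 10% in the one open tail:
- 0/10: 1 − 0.10^(1/10) = 0.2057.
- 10/10: 0.10^(1/10) = 0.7943.

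These are the printed values. So one composite rule, 5% per tail for counts 1 to 9 and 10% in the open tail at 0 and n, reproduces all 22 printed limits. (A mid-P limit also gives 0.206 at 0/10, but only because 0.5(1−p)^10 = 0.05 is the same equation as (1−p)^10 = 0.10. Mid-P matches none of the 18 limits in the other rows; at 1/10 it gives 0.010 to 0.350.)

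**Step 4: coverage of the composite rule.** Coverage at a true rate p is the probability of the counts whose interval contains p. For p between 0.2057 and 0.2224, the 0/10 interval no longer reaches p and the 5/10 interval (lower limit 0.2224) does not yet include it. Only counts 1 to 4 cover, so coverage = P(X ≤ 4) − P(X = 0).
- p = 0.2057: 0.9633 − 0.1000 = 0.8633.
- p = 0.2224: 0.9500 − 0.0808 = 0.8692.

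With 0.259 as the upper limit, 0/10 also covers, and coverage over the same range is P(X ≤ 4), from 96.3% down to 95.0%. By symmetry the same holds for p from 0.7776 to 0.7943.

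On a grid of step 0.00005, the composite rule is below 90% only in these two bands, which together span 2 × (0.2224 − 0.2057) = 0.033 of the 0-1 range. Clopper-Pearson throughout never falls below 92.3%.

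**The case against.** The best defence is that nothing has been miscalculated. Putting the whole error in the open tail when the other limit is fixed at 0 or 1 is a known convention, and the end values are correct one-sided 90% bounds: 0.794^10 is about 0.10. No section demands 5% per tail, so the two limits are too tight only relative to the other nine rows. All of that stands. A reader might infer that the two cells are arithmetic slips, or that no coherent rule lies behind the table; Step 3 shows otherwise.

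The defence also holds that the practical effect is slight, and this stands too. At assumed true rates of 5%, 10% and 20%, 0/10 would occur with probability 59.9%, 34.9% and 10.7%, but all three rates lie inside the printed interval, and coverage is the same under both rules (98.8%, 98.7% and 96.7%). At 25% the printed table still covers 92.4%. The upper band, 77.8-79.4%, lies far above the highest response rate the protocol cites for this drug (25.4%, section 1.2.1.4.2), and at a true rate of 25% the chance of 10/10 is about one in a million.

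It may be tempting to argue that the choice reverses a conclusion, because 0.206 excludes a 25% response rate and 0.259 does not. The documents do not support that. The statement that "an ORR of at least 25% would be considered promising in this patient population" belongs to the Cohort 1 design; Cohorts 2 and 3 have no target or threshold.

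What the defence does not answer is that the convention is stated nowhere and that, combined with equal-tail limits in the other rows, it yields a procedure that misses its own label over part of the range.

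**Conclusion.** The point holds as an unstated mixed-tail rule with a small effect. Nine rows use 5% per tail, two use 10% in one tail, and all eleven carry the same label. Taken as one procedure the table is not a 90% interval everywhere: coverage falls to 86.3-86.9% for true response rates of about 20.6-22.2% and 77.8-79.4%, where a consistent exact method covers 95.0-96.3%.

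Two assumptions underlie this. The first is that Clopper-Pearson is the intended method; it is read back from the nine matching rows, since the plan does not name it. The second is that the final analysis would follow the table, including its end rows.

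No decision, sample size or test depends on the two rows, and the Cohort 1 Simon design is unaffected. It is a minor correction, worth making before data are seen because it concerns the primary-endpoint interval.

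**What to change.** In the section 10.1 table, replace the 0/10 row with (0.000, 0.259) and the 10/10 row with (0.741, 1.000). In section 10.4.1, and for the repeated interval in 10.4.2, state that the 90% response-rate intervals for every cohort are two-sided Clopper-Pearson with 5% per tail at every count, including 0 and n. The sentence should cover Cohort 1 as well, because 10.4.1 promises the interval for each cohort.

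If the one-tail convention at 0 and n was intended, footnote it under the table, state it in the same two sections, and acknowledge the coverage shortfall.

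The cost is two table rows and a sentence naming the method. The only downside is that the stated precision at 0/10 and 10/10 becomes 5.3 percentage points less favourable at the open limit.

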10.2 Data analysis populations set

Full Analysis Set

The Full Analysis set (FAS) includes all patients who received at least one dose of Infigratinib. The FAS will be used for all listings of raw data. Unless otherwise specified, the FAS will be the default analysis set used for all analyses.

Safety Set

The Safety Set includes all patients who received at least one dose of Infigratinib and have at least one valid post-baseline safety assessment. The statement that a patient had no AE (on the AE eCRF) constitutes a valid safety assessment.

Per-Protocol Set

The Per-Protocol Set (PPS) will consist of a subset of patients in the FAS who are compliant with requirements of the Clinical Study Protocol (CSP) in the following ways:

- Patient had an adequate tumor assessment at baseline
- Patient is evaluable for efficacy or discontinued due to adverse event, Investigator's decision, patient's refusal, disease progression, or died prior to the first evaluation of the primary efficacy variable
- Patient had no major protocol deviations.

Patients will be evaluable for efficacy if they have at least one response assessed differently from 'unknown' or 'not assessed' as per RECIST v1.1. All major protocol deviations leading to exclusion from the PPS will be detailed and summarized.

10.3 Treatments (study treatment, concomitant therapies, compliance)

Study treatment

The actual dose and duration in days of Infigratinib treatment as well as the dose intensity (computed as the ratio of actual dose received and actual duration) and the relative dose intensity (computed as the ratio of dose intensity and planned dose received/planned duration), will be listed and summarized by means of descriptive statistics. The summary data will be presented for all study days as a single category. The FAS will be used.

Concomitant therapies

Concomitant medications and significant non-drug therapies prior to and after the start of the study drug treatment will be listed by patient and summarized.

Compliance

Compliance to the protocol will be assessed by the number and proportion of patients with protocol deviations. These will be identified prior to database lock and will be listed and summarized. Compliance to the study drug will be assessed by the number of dose reductions and dose interruptions.

10.4 Efficacy analysis

10.4.1 Primary endpoint: ORR

Analysis of the efficacy primary endpoint (ORR) will be conducted when all patients have completed at least 6 cycles of treatment or have discontinued from the trial. Any PR or CR until the data cut-off date will be considered as a responder for ORR, irrespective of when it occurred. The following analysis will be done for each cohort of patients.

The estimated ORR will be presented along with the corresponding 90% confidence interval for each cohort, based on a binomial distribution.

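### The 90% CI table for Cohorts 2 and 3 in Section 10.1 uses one-sided limits in its 0/10 and 10/10 rows and two-sided limits elsewhere; the interval method should be named and used throughout

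*Combined protocol and SAP*

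**What the plan says.** Section 10.4.1 plans the same kind of interval for all three cohorts: "The estimated ORR will be presented along with the corresponding 90% confidence interval for each cohort, based on a binomial distribution". Section 10.4.2 repeats this under best overall response: "The estimated ORR and corresponding 90% confidence intervals based on the binomial distribution will be reported". The data analysis entry of the Protocol Summary also promises a 90% interval for each cohort, without naming a distribution. None of the three places names the method.

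Section 10.1 tabulates the 90% interval for every possible count out of 10 evaluable patients in Cohorts 2 and 3. For 0 responses it prints 0.0 to 0.206, and for 10 responses 0.794 to 1.000.

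For Cohort 1, Section 10.1 sets a Simon two-stage design with a 5% null and a 25% target. The stopping rule is: "After evaluating 9 patients enrolled in the first stage, the trial will be terminated if 0/9 patients demonstrate a response". Otherwise 30 evaluable patients are enrolled, and the success rule is: "If the total number responding is 4 or more, then the drug demonstrates promising response in this patient population". The stated properties are: "This design has 90% power and 5% type I error".

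**The concern.** The table is the only evidence of which binomial interval is meant, so an analyst is likely to copy its convention. If its rows follow two rules, the reported interval does not have its nominal 90% level over part of the range. The rows affected are the ones that matter most when a small cohort shows nothing. At 0/10 the printed upper limit of 0.206 lies below the 25% that Section 10.1 calls promising for Cohort 1; the limit under the other rows' rule, 0.259, lies above it. The same choice would arise if Cohort 1 stopped at 0/9.

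A second, smaller question is whether a plain binomial interval for Cohort 1 agrees with the two-stage count rule. A two-sided 90% interval has 5% in each tail, which matches the 5% type I error, so a reader will expect the two to agree.

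**Working it through.** **Inputs.** Section 10.1: n=10 for Cohorts 2 and 3; for Cohort 1, null 5%, target 25%, stop at 0/9, total 30, success at 4 or more. Section 10.4.1: 90% level.

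**1. The table's convention.** A two-sided 90% Clopper-Pearson interval solves P(X ≥ x) = 0.05 for the lower limit and P(X ≤ x) = 0.05 for the upper.

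| Responses | Clopper-Pearson, 5% per tail | Printed |
|---|---|---|
| 1/10 | 0.005, 0.394 | 0.005, 0.394 |
| 2/10 | 0.037, 0.507 | 0.037, 0.507 |
| 5/10 | 0.222, 0.778 | 0.222, 0.778 |
| 9/10 | 0.606, 0.995 | 0.606, 0.995 |
| 0/10 | 0, 0.259 | 0.0, 0.206 |
| 10/10 | 0.741, 1 | 0.794, 1.000 |

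Rows 3, 4, 6, 7 and 8 also reproduce to three decimals. The end rows have closed forms:
- 5% in the tail: 1 − 0.05^(1/10) = 0.259, and 0.05^(1/10) = 0.741.
- 10% in the tail: 1 − 0.10^(1/10) = 0.206, and 0.10^(1/10) = 0.794, which are the printed values.

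**2. Effect on coverage at n=10.** Take a true ORR just above 0.2057.
- With the printed rows, 0/10 misses it (upper limit 0.2057), and so do 5/10 and above (lower limits from 0.222). Only 1 to 4 responses cover it.
- P(1)+P(2)+P(3)+P(4) = 0.2589 + 0.3017 + 0.2083 + 0.0944 = 0.8633. This 86.3% is the minimum over all rates.
- With 0.259 in the 0/10 row, P(0) = 0.1000 is added and coverage there is 0.963. The minimum over all rates becomes 92.3%, near ORR 30%.
- The shortfall below 90% runs from about 0.206 to 0.222, where the 5/10 row starts to cover, and by symmetry from 0.778 to 0.794.

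**3. Cohort 1 stop at 0/9.** With 5% in the tail the upper limit is 1 − 0.05^(1/9) = 0.283; with 10% it is 1 − 0.10^(1/9) = 0.226. With Clopper-Pearson for all stage 2 results, coverage under the two-stage design is:

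| 0/9 upper limit | ORR 5% | ORR 20% | ORR 25% | Minimum |
|---|---|---|---|---|
| 0.283 | 98.6% | 95.4% | 95.5% | 89.2% (ORR 28.35%) |
| 0.226 | 98.6% | 95.4% | 88.0% | 84.7% (ORR 23.9%) |

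**4. Cohort 1 at 4/30.** The plan's own figures reproduce first. P(continue and total ≥ 4) is 0.0489 at 5% and 0.9019 at 25%, matching the stated 5% and 90%. The stop is what brings the error below 5%:
- Fixed-n tail P(X ≥ 4 of 30 at 5%) = 0.0608.
- Part removed by the stop: P(0/9) × P(≥ 4 of 21) = 0.6302 × 0.0189 = 0.0119.
- 0.0608 − 0.0119 = 0.0489.

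Because the fixed-n tail at 5% exceeds 0.05, the Clopper-Pearson lower limit at 4/30 must fall below 5%. The interval is 0.0469 to 0.2796. At 5/30 the lower limit is 0.068, so the mismatch is confined to 4/30. That outcome has probability 3.5%, 10.4% and 4.7% at true ORR 5%, 20% and 25%. Lower limits at 4/30 by other methods are Wilson 0.061, Jeffreys 0.057 and mid-P 0.054 (all exclude 5%), and Wald 0.031 (includes it).

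**5. Two-stage exact interval.** Inverting the two-stage tail probabilities, with the 0/9 stop ordered lowest and then total responses, gives 0.0504 to 0.3129 at 4/30. Upper limits at lower counts:

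| Result | Clopper-Pearson | Two-stage exact |
|---|---|---|
| 1/30 | 0.149 | 0.283 |
| 2/30 | 0.195 | 0.286 |
| 3/30 | 0.239 | 0.295 |

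With other stage sizes, four responses give p = 0.0531 (9, then 31 in total) and p = 0.0513 (10, then 30 in total).

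**The case against.** At 0/10 the interval can miss on one side only, so putting the whole 10% in one tail is a recognised choice, and the table is only a planning illustration. Both statements are fair. But the choice keeps 90% coverage only if the other rows allow for it, and here they spend 5% per tail, so the combination falls to 86.3%. The plan also contains no other guide to the method.

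On Cohort 1, a reader might infer that the planned interval is invalid because it ignores the 0/9 stop, or that the trial's error rate is affected. The documents do not support either reading. Success is decided by the count of responses, and nothing ties the interval to the 5% null. With the 0.283 limit at 0/9, coverage is adequate: 95% or more at 5%, 20% and 25%, and 89.2% at its lowest. The 84.7% minimum needs the table's end-row rule to be carried over to 0/9, which the plan does not say. The mismatch at 4/30 needs a method the plan does not name and exactly 4 responses in 30, and its size is 0.3 percentage points.

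A reader might also infer that a two-stage exact interval is required. That is a trade-off. It repairs 4/30, but every stage 2 result that is not promising would then carry an interval that includes 25%, which Clopper-Pearson excludes in all three cases. Its agreement with the count rule also fails at some nearby stage sizes.

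**Conclusion.** The table is wrong as printed: two of its eleven rows break the convention of the other nine. If the convention is followed in the analysis, a nominal 90% interval has minimum coverage of 86.3% instead of 92.3%, with the shortfall below 90% confined to true rates of about 0.206 to 0.222 and 0.778 to 0.794. This needs no assumption about Cohort 1.

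The Cohort 1 point is secondary and affects reporting only. The decision rule, its 0.0489 type I error and its 90.2% power are unchanged. It rests on Clopper-Pearson being the intended method, which is inferred from rows 1 to 9 of the table, and on exactly 30 analysed patients. The second assumption is not secure: Section 10.1 counts evaluable patients, while Section 10.2 says "Unless otherwise specified, the FAS will be the default analysis set used for all analyses".

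**What to change.** - In the Section 10.1 table, change 0/10 to (0, 0.259) and 10/10 to (0.741, 1).
- In Section 10.4.1, name the two-sided 90% Clopper-Pearson interval with 5% per tail, including at zero and full response. State that a Cohort 1 stop at 0/9 uses the same rule (upper limit 0.283). Refer to this from Section 10.4.2 and the Protocol Summary.
- For Cohort 1, state that the count rule governs the conclusion and that the interval is descriptive. Report beside it the one-sided p-value from the two-stage distribution, computed from the actual stage sizes (0.0489 at 4/30 with stages of 9 and 30), and state the denominator used.
- Optionally, add the two-stage exact interval as a supplement, with its ordering stated and a note that it can disagree with the count rule off the planned sizes.

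The cost is two table cells, a few sentences and a few lines of code. No patients, data or decision rules change. The wording should be fixed before the response counts are known, because at 4/30 the choice of method decides whether the interval excludes 5%.
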